PROTOCOL TITLE: Broadening the Reach, Impact, and Delivery of Genetic Services (BRIDGE)

NCT NUMBER: NCT03985852

PROTOCOL DATE: 06/05/2019

The full trial protocol is available at:

[name], [name], [name], et al. Comparing models of delivery for cancer genetic services among patients receiving primary care who meet criteria for genetic evaluation in two healthcare systems: BRIDGE randomized controlled trial. *BMC Health Sciences Research*. 2021;21:542. doi:10.1186/s12913-021-06489-y

Date: Tuesday, August 6, 2024 10:49:19 AM

[Print](#)[Close](#)**IRB_00123563****Created:** 6/5/2019 3:01 PM**PI:** [name]**Submitted:** 3/5/2019**Title:** Broadening the Reach, Impact, and Delivery of Genetic Services**IRB_00123563**

1. Contacts and Title

1. Study Introduction

1. Responsible Investigator:

[name]

Email	Training	Col Date
[contact]	4/25/2022 SMCG	3/19/2024

a. Position of the Investigator:

Faculty or Non-Academic Equivalent

Student

Staff

Resident/Fellow

Other

2. Contact Persons for the Responsible Investigator:

Name	Email	Training
[name]	[contact]	2/22/2023 MCG
[name]	[contact]	3/4/2024 SMCG
[name]	[contact]	3/21/2022 SMCG
[name]	[contact]	1/9/2023 SMCG

3. Guests of the Responsible Investigator:

Last Name	First Name	E-Mail
[name]	[contact]
[name]	[contact]
[name]	[contact]
[name]	[contact]
[name]	[contact]

4. What type of application is being submitted?

New Study Application (or Amendment/Continuing Review)

5. Title Of Study:

Broadening the Reach, Impact, and Delivery of Genetic Services

6. Study Purposes and Objectives:

The proposed study will employ an implementation science framework to compare two models of genetic services delivery for 1,920 patients in a randomized controlled trial with clinic-level randomization. We hypothesize that uptake of genetic testing (Study Aim 2) and adherence to management recommendations (Study Aim 3) will be equivalent between the genetic services delivery models. We propose the following Specific Aims:

Aim 1) Identify primary care patients who qualify for genetic risk assessment in two healthcare systems using a CDS infrastructure to automatically evaluate family history.

*This aim has already been studied in IRB #105797. We will be utilizing this tool that is now available. Aim 1 will not be analyzed in this protocol but is part of our overall research model.

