Research Aims to be studied in this protocol:

Aim 2) Compare uptake of genetic testing for patient-directed standard of care vs. enhanced standard of care genetic services delivery models for 1,920 unaffected primary care patients. We will utilize a randomized trial design with clinic-level randomization to compare two standard of care models: a *patient-directed standard of care* model and an *enhanced* model. In the *patient-directed* model those identified by the clinical decision support (CDS) infrastructure as meeting testing criteria will be informed of their cancer risks, provided with educational resources, and offered the option to select genetic testing through a patient portal. This online portal will be overseen by HCI genetic counselors. The *enhanced standard of care* model in which primary care providers and patients are notified through CDS when criteria are met (the *enhancement* of standard of care) and of the availability of standard of care genetic services. We will compare uptake of genetic testing by model and by race/ethnicity and rurality.

Aim 3) Compare adherence to recommendations and other patient responses for the genetic services delivery models. We will compare the effects of the genetic services delivery models on adherence to management recommendations at 12 months after return of results, or last genetic services contact. We will assess cognitive (i.e., recall, comprehension, uncertainty, risk perceptions) and affective (i.e., test-related distress, positive reactions, decision regret) responses at 4 weeks, and communication (i.e., family, provider) interactions at 4 weeks and 12 months after last genetic services contact. We will also examine differences in effects by race/ethnicity and rurality.

7. Is this a multi-site study, where more than one site needs IRB approval?

Yes No

8. Background and Introduction:

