Research Procedures

1. A research coordinator or genetic counseling assistant will determine who is eligible to participate in the research procedures based on participation in genetic services and access to MyChart, the patient portal. A waiver of recruitment is being requested for this authorization. Up to 20,000 unique electronic health records may be accessed to determine inclusion in this study, and basic health outcomes tracked for comparison.
2. Consent cover letter will be sent via patient portal to offer participation in this research study, with a link to an online questionnaire. The consent cover letter will be sent to patients approximately 4 weeks after genetic test results are returned for those who decide to test and about 8 weeks after participation in pre-test genetic counseling services for those who decide not to test.

If no response is received to the first message, after 1 week another message in the patient portal will be sent. If still no response up to 3 phone calls will be made.

3. Online questionnaires will utilize REDCap, which has a HIPAA-compliant interface. Estimated 960 patients will be offered participation through University of Utah Health; 1,960 patients over both participating sites.

i. **Questionnaire #1:** At about **4 weeks after return of results for those who decide to test** (8 weeks after pre-test genetic counseling), we will assess cognitive (i.e., recall, comprehension, uncertainty, risk perceptions), affective (i.e., test-related distress, positive reactions, decision regret), communication (i.e., family, provider) responses, experience with genetic counseling, and sociodemographic characteristics including numeracy for those who decide to test. For those who do not decide to test, we will assess experience with genetic counseling, reason for not testing, decision regret, risk perceptions, and sociodemographic characteristics including numeracy.

ii. **Questionnaire #2:** At about **12 months**, we will ask about discussion of their test results with their PCP, family members, or others, and self-reported use of cancer screenings for those who decide to test. We will also utilize EHR data to examine adherence to recommendations. For those who decide not to receive genetic testing, we will assess the self-reported use of cancer screenings, whether genetic testing was pursued at another time or through another source, communication with family members and whether other relatives had testing.

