iii. After each returned questionnaire, participants will be compensated via the patient portal with a thank you message and a \$10 e-gift card. This totals \$20 dispersed if both questionnaires are returned.

iv. For any participants who would like to complete questionnaires by telephone, a genetic counseling assistant or research coordinator will administer the questionnaire. Calls will be digitally recorded to allow for analysis of comprehension. Each questionnaire will take about 15 minutes to complete. Participants may also complete the questionnaires by mail if they choose.

4. Study staff will track the EHR of participants who were identified by the CDS algorithms. Any screenings, care or health procedures related to genetic services will be recorded in the research record to determine if an impact is made because of participation in genetic services. This is estimated to be up to 20,000 individual records in the EHR.
5. Data analysis for outcome data will occur after patient enrollment is complete. Patients who return questionnaires will be compared to similar cohorts that were not directly involved with research questionnaires.

More specific details of data analysis are outlined in the statistical methods section.

7. Are all procedures for research purposes only (non-standard or non-standard of care procedures)?

Yes No

If no, list the procedures that are performed for research purposes only (non-standard or non-standard of care procedures):

Questionnaire #1: estimated 4-8 weeks from last genetic services contact (4 weeks for those who decide to test and 8 weeks for those who decide not to test)

Questionnaire #2: estimated 12-months from last genetic services contact

Data Analysis of genetic services impact and outcomes

8. Is there a safety monitoring plan for this study?

Yes No

9. Provide a summary of the statistical methods, data analysis, or data interpretation planned for this study. Factors for determining the proposed sample size (e.g., power) should be stated.

Research Aims Analysis for this specific IRB:

Aim 2 Analysis.

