Aim 2 analyses will address the dimensions of Reach, Effectiveness, Adoption, and Implementation from our conceptual framework. For Effectiveness, we will be testing for equivalence between study arms in uptake of genetic testing. We will check randomization by comparing demographic characteristics between patients in the two arms. Any characteristic(s) that are significantly different will be controlled for in the multivariable analysis. We will examine descriptive statistics, and will use Fisher's Exact test with a two-sided 0.05 significance level for univariate comparison of proportions to examine the association between study arm and uptake of genetic testing. We will next build multilevel multivariable logistic regression models to examine the effect of study arm on the outcome controlling for clinic-level (clinic type, patient volume, patient composition, number of providers), provider-level (specialty, years in practice, gender), and patient-level (e.g., sociodemographic, clinical) variables. We will examine the intra-class correlation (ICC) by clinic and provider. If a significant ICC is observed, the regression models will be extended to include random effects for clinic or provider, and fit using software for generalized mixed models. Covariates will be included in models if significant in unadjusted analyses. For Reach, using the multivariable regression models with interaction terms, we will examine whether the effects of study arm on uptake of genetic testing is modified by race/ethnicity or rurality. For Adoption, we will examine the proportions of providers and patients who access educational resources and with referrals, and whether this differs by population subgroup. For Implementation, we will assess responses to patient portal messages and completion of study workflows. Statistical significance will be assessed as $p < 0.05$; SAS 9.4 and/or Stata 15.1 will be used for analysis.

Aim 2 Sample Size

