
 Yes No**12. Any component of the Clinical and Translational Science Institute (CTSI)?** Yes No**The Clinical Research Center (CRC)?** Yes No

IRB_00123563

Created: 6/5/2019
3:01 PM

IRB_00123563

- Request for Waiver of Authorization

PI: [name]

Submitted: 3/5/2019

Title: Broadening the Reach, Impact, and
Delivery of Genetic Services**Request for Waiver or Alteration of Authorization****Request for Waiver of Authorization for Recruitment Only**

This option must only be used if you are reviewing PHI in order to identify eligible participants BEFORE approaching them to obtain consent and authorization. All other waiver requests must be entered below.

Waiver of Authorization for Recruitment Requested**Other Requests for Waivers of Authorization:**

- *Click "Add" below to add a new waiver request to this application.*
- *Click the waiver name link to edit a waiver that has already been created.*
- *To delete a waiver request, contact the IRB.*

Date Created	Type of Request	Purpose of Waiver Request
View 2/21/2019	Waiver of Authorization	Waiver of Authorization for access to EHR for chart review of patients that are identified by CDS tool for inclusion/exclusion criteria. This would be to track patients utilizing genetic services up to 24 months to assess the impact of genetic services on their health and/or health decisions.
View 3/18/2019	Waiver of Authorization	Waiver of authorization to not include authorization language in the consent cover letter.

IRB_00123563

Created: 6/5/2019
3:01 PM

IRB_00123563

Waiver of Authorization for Recruitment Only

PI: [name] ScDSubmitted:
3/5/2019**Title:** Broadening the Reach, Impact, and Delivery of Genetic Services

Request for Waiver or Alteration of Authorization

Request for Waiver of Authorization for Recruitment Only

The PI must agree to the terms of this waiver request as described on this page. When the PI uses the "Submit" activity to submit the application for IRB review, a checkbox to accept the terms will be available in the "Submit" activity window.

This waiver request includes justification for waivers of consent for recruitment only, according to 45 CFR 46.116(d).

Terms for the Waiver of Authorization:

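### Aim 3 adherence: no screening status before identification is specified as a data item or covariate, so prior habit adds avoidable variance and an arm difference in it would go unseen

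*Combined protocol and SAP*

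**What the plan says.** Study Purposes and Objectives hypothesises that "adherence to management recommendations (Study Aim 3) will be equivalent between the genetic services delivery models". Aim 3 places the outcome as "adherence to management recommendations at 12 months after return of results, or last genetic services contact".

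Under 4. Study Information, item 6 (Research Procedures), both questionnaires follow the delivery of services. The topics listed for Questionnaire #1 do not include screening. Questionnaire #2, at about 12 months, covers "self-reported use of cancer screenings for those who decide to test. We will also utilize EHR data to examine adherence to recommendations"; patients who decline testing also report screening at that time. Of the chart tracking, Procedure 4 says: "Any screenings, care or health procedures related to genetic services will be recorded in the research record". The chart-review waiver of authorization is meant to "track patients utilizing genetic services up to 24 months", with no start point given. The data lists in the consent waiver and in both authorization waivers include the date of the last appointment and other health conditions, but not screening history.

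Under item 9, the Aim 2 Analysis says: "We will check randomization by comparing demographic characteristics between patients in the two arms". Models may draw on "patient-level (e.g., sociodemographic, clinical) variables", but a covariate enters only on significance: a significant arm difference in the balance check, or significance in an unadjusted analysis. A clinic or provider random effect is added only if the ICC is significant. The Aim 3 Analysis adopts the same model-building procedure.

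**The concern.** The participants are primary care patients aged 25 to 60 with a qualifying family history, and some will already be in screening. What a patient did before identification is likely to be the strongest predictor of what the record shows a year later. If it is not collected, three things follow.

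- The adherence contrast carries variance that a routine baseline covariate would remove.
- Questionnaire eligibility depends on having taken part in genetic services. That happens after clinics are randomised and is reached by different routes in the two arms: a counselling visit or the portal. Patients who reach Aim 3 could differ in prior screening by selection as well as by chance, and a demographic balance check would not show it.
- The EHR tracking is meant to show whether participation had an impact. Without prior status, a response to the recommendation is hard to tell from existing habit.

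**Working it through.** **1. The plan's own figure.** Aim 3 states that 1,100 patients give more than 90% power for an effect size of 0.02, with 2 tested variables, 20 adjusters and alpha 0.05. With a noncentral F, λ = 0.02 × 1,100 = 22 and df = 2 and 1,100 − 23 = 1,077, power is 99.1%. With the 15-per-clinic design effect from the Aim 2 inputs, 1 + 14 × 0.05 = 1.70, the effective size is 1,100/1.70 = 647 and power is 90.5%. The stated figure reproduces. It does not depend on baseline screening, so nothing below overturns it.

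**2. Inputs for the baseline difference.**
- From the documents: 1,100 patients (Aim 3 Sample Size); 32 and 16 clinics, and an ICC of 0.05 (Aim 2 Sample Size).
- Assumed: equal split, 550 per arm; share up to date at baseline p = 0.3 to 0.7; a second ICC of 0.01, because the plan calls its 0.05 a likely overestimate and chose it for testing uptake, not screening.

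**3. Formula.** SD = √{p(1−p) × [DE₁/n₁ + DE₂/n₂]}, with DE = 1 + (m−1) × ICC. Clinic sizes are m = 550/32 = 17.2 and 550/16 = 34.4.

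| ICC | DE, 32 clinics | DE, 16 clinics | SD at p = 0.3 or 0.7 | SD at p = 0.5 | Chance of a gap of 5 points or more |
|---|---|---|---|---|---|
| 0.01 | 1.16 | 1.33 | 3.1 points | 3.4 points | 11% to 14% |
| 0.05 | 1.81 | 2.67 | 4.1 points | 4.5 points | 23% to 27% |

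For example, at ICC 0.05 and p = 0.5: 0.25 × (1.81 + 2.67)/550 = 0.00204, and the square root is 0.045.

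The continuing review submitted in January 2024 counts 335 patients who completed either questionnaire. If these were split equally over the same clinics, the SD at ICC 0.05 would be 5.8 to 6.3 points. EHR-based adherence may be available for more patients.

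**4. Gain from adjustment.** The standard error is multiplied by about √(1−r²). For r = 0.3 this is √0.91 = 0.954, a cut of about 5%. For r = 0.6 it is √0.64 = 0.80, a cut of 20%. This holds on the risk-difference scale and assumes that r applies within and between clinics. The values of r are assumed.

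**5. What rescoring can and cannot do.** The adherence rule is not stated, so this step is illustrative. Let b be the share already up to date and not due, and suppose 60% of those due are screened in both arms, so there is no true effect. Let b be 0.35 in one arm and 0.45 in the other.
- Counting only new procedures: 0.65 × 0.6 = 0.39 against 0.55 × 0.6 = 0.33, a spurious 6 points.
- Counting up-to-date patients as adherent: 0.35 + 0.39 = 0.74 against 0.45 + 0.33 = 0.78, a spurious 4 points the other way.

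Neither rule removes the imbalance. Adjusting for baseline status, or restricting to patients who are due, does.

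**The case against.** A reader might infer that patients already up to date will be scored as non-adherent. The documents do not support this. They contain no rule that only a procedure done after services counts. They speak of adherence to recommendations, which are tailored letters, and a patient who is current and not yet due could count as adherent. If such patients were scored non-adherent in both arms, a true 10-point difference among those due would shrink to 6 points when 40% are up to date, which favours equivalence. That is conditional on a rule nobody has written down.

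A reader might also infer that a look-back is ruled out. It is only unspecified. The EHR tracking has no stated start date, the questionnaires are separate attachments whose recall window is not visible here, item 9 asks only for a summary of methods, and the full trial protocol is published elsewhere.

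A third tempting reading is that chance differences between clinics bias the comparison. They do not. Randomisation balances prior habit in expectation across the patients of the randomised clinics, and a cluster-aware standard error already contains this variation; the SDs above are not an error to be added to it. Clinical covariates are also permitted, so prior screening could enter.

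All three points stand. They leave untouched that nothing secures the covariate: it is not on any data list, it would have to pass a significance screen, and the random effect that would carry the clinic variation depends on a significance test too. Nor does randomisation protect a comparison limited to patients who went on to use services.

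**Conclusion.** The concern holds as a design improvement, not as a demonstrated error. The plan as written specifies no screening status before identification for an outcome on which it hypothesises equivalence. The cost is avoidable variance: a standard error larger than necessary, which adjustment would cut by about 5% to 20% if baseline status correlates 0.3 to 0.6 with the outcome. There is also a blind spot, since an arm difference in prior screening among patients reaching Aim 3 would go unseen. The size of a chance difference (SD 3.1 to 4.5 points over the two ICCs) rests on an assumed baseline rate of 0.3 to 0.7, because the documents give none. Whether up-to-date patients are misclassified cannot be determined until adherence is defined, and no stated sample size or power figure changes.

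**What to change.** - In item 6, Research Procedure 4, and in the three waiver data lists, add the date of the last screening of each relevant type before CDS identification, taken from the EHR records already accessed.
- Define baseline screening status from those dates over a fixed look-back period. It must not depend on the recommendation, which is issued only after services.
- State the adherence rule, the recall window of the self-report items and the start and end of the EHR window. Screening intervals are for the investigators to set.
- In the Aim 3 Analysis, include baseline status in the adherence model whatever its p-value, and show it by arm among patients analysed.
- As a sensitivity analysis, restrict to patients not already up to date at identification.

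The cost is one retrospective query, one line in each waiver and a few sentences of analysis text. No extra patients are needed, and closed accrual at Utah is no obstacle. The query must precede the destruction of identifiers at study closure. The continuing review submitted in January 2024 says analysis of the primary outcomes is under way, so if adherence by arm has already been seen, the adjusted analysis should be labelled post hoc. Screening done outside the health system may be missed in both arms. The restricted analysis is smaller: with 30% to 70% up to date, 1,100 × 0.7 = 770 down to 1,100 × 0.3 = 330 patients remain.

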Sample size for Aim 2 was calculated using PASS 15 based on an equivalence test for the difference of two proportions in a cluster-randomized design. Sample sizes of 480 in the patient-directed arm and 480 in enhanced standard of care arm, which were obtained by sampling 32 clusters (clinics) with 15 participants each and 16 clusters (clinics) with 30 participants each, respectively, achieve 80% power to detect equivalence. The margin of equivalence, given in terms of the difference between proportions, extends from -0.10 to 0.10. The calculations assume Likelihood Score Tests (Farrington & Manning) were used with an ICC of 0.05, and a significance level of 0.05. We believe that this is likely an overestimate of ICC based on our prior work. This sample size is sufficient for a multilevel multivariable regression analysis and achieves >95% power to detect a small effect size (0.02) attributable to 1 independent variable using an F-Test with an alpha of 0.05, adjusted for an additional 20 independent variables. To examine effect modification, sample size is calculated based on logistic regression of a binary response variable (Y) on a binary independent variable (X) and a binary confounder variable (Z). A sample size of 1,710 observations achieves 80% power at a 0.05 significance level to detect the X-Z interaction odds ratio of 1.5, using a two-sided Wald test. We will therefore enroll 1,920 patients in the Aim 2 trial to allow for about 10% attrition.

Aim 3 Analysis

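### Aim 2 is declared and sized as an equivalence comparison, but the ±0.10 margin never reaches the analysis text, which names only tests of no difference

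*Combined protocol and SAP*

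**What the plan says.** All references are to the combined protocol and SAP.

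- **Goal.** Study Purposes and Objectives hypothesises that uptake (Aim 2) and adherence (Aim 3) are equivalent between the models. The Aim 2 Analysis repeats it: "we will be testing for equivalence between study arms in uptake of genetic testing".
- **Sizing.** Under Aim 2 Sample Size, the calculation is "based on an equivalence test for the difference of two proportions in a cluster-randomized design". The margin is set on the risk-difference scale: "The margin of equivalence, given in terms of the difference between proportions, extends from -0.10 to 0.10". The test, ICC and level used for sizing come next in that section: "The calculations assume Likelihood Score Tests (Farrington & Manning) were used with an ICC of 0.05, and a significance level of 0.05". On the ICC the authors add: "We believe that this is likely an overestimate of ICC based on our prior work". They do not say whether the 0.05 significance level is per side or total, and they give no expected uptake.
- **Analysis.** The first arm comparison in the Aim 2 Analysis, with uptake as the outcome, is Fisher's test: they "will use Fisher's Exact test with a two-sided 0.05 significance level for univariate comparison of proportions to examine the association between study arm". Multilevel logistic models for the effect of arm follow. On clustering: "If a significant ICC is observed, the regression models will be extended to include random effects for clinic or provider". The only criterion stated is p below 0.05.
- **Aim 3.** The Aim 3 Analysis uses t, Wilcoxon, chi-square or Fisher tests and regression. No margin is given for adherence.

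**The concern.** An equivalence claim needs a null hypothesis that the arms differ by at least the margin, and evidence that rejects it. Both comparisons named in the Aim 2 Analysis have the opposite null, that the arms do not differ. Fisher's test also treats patients as independent although clinics were randomised. The logistic models report odds ratios, and nothing links them to a margin set on the difference in proportions.

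An analyst who follows the section as written never compares an interval, or a pair of one-sided tests, with ±0.10. The main Aim 2 conclusion could then be drawn from p-values that answer a different question. The error can go either way: a non-significant result taken as equivalence when a 10-point gap exists, or a significant result taken as a failure of equivalence when the difference is demonstrably inside the margin.

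**Working it through.** **1. Inputs.** From Aim 2 Sample Size: 32 clinics of 15 (patient-directed) and 16 of 30 (enhanced), 480 per arm, ICC 0.05, margin ±0.10, level 0.05, 80% power, planned total 1,920. Assumed: all uptake rates, ICCs of 0.01 and 0.02, and an even split to 960 per arm over the same clinics (32 × 30 and 16 × 60).

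**2. The plan's own figure.** Design effect = 1 + (m - 1) × ICC, so 1 + 14 × 0.05 = 1.70 and 1 + 29 × 0.05 = 2.45. With no true difference and common uptake p, SE = √[p(1-p)(1.70 + 2.45)/480], and power ≈ 2Φ(0.10/SE - 1.645) - 1.
- p = 0.16: SE = √(0.1344 × 4.15/480) = 0.0341; power = 2Φ(1.29) - 1 ≈ 80%.
- p = 0.30: SE = 0.0426; power ≈ 52%.
- p = 0.50: power ≈ 39%.

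With 1.96 in place of 1.645 (0.025 per side), 80% needs uptake of about 12%. The stated power is therefore attainable, but only at uptake near 12-16%, so low uptake belongs among the scenarios.

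**3. True gap of 10 points (not equivalent), 960 per arm, ICC 0.05.** Simulation with beta-binomial clinics. The cluster-adjusted test is a clinic-level Satterthwaite t-test; the rule is a clinic-level 90% CI wholly inside ±0.10. Uptake is patient-directed vs enhanced.

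| Uptake, % | Fisher non-significant | Cluster-adjusted non-significant | CI rule wrongly passes |
|---|---|---|---|
| 15 vs 5 | 0.1% | 1.7% | 4.7% |
| 20 vs 10 | 1.0% | 8.0% | 4.6% |
| 10 vs 20 | 0.8% | 8.6% | 5.8% |
| 30 vs 20 | 4.3% | 20.6% | 4.5% |
| 20 vs 30 | 4.1% | 22.4% | 5.2% |
| 50 vs 40 | 9.0% | 33.1% | 4.8% |
| 40 vs 50 | 8.5% | 33.3% | 4.6% |

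At lower ICC the cluster-adjusted column shrinks. For the last four rows it is 5-13% at ICC 0.02 and 1-5% at 0.01; for the first three it is under 1% at 0.02.

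**4. True gap of 5 points (inside the margin), 960 per arm.** Share of trials in which the cluster-adjusted test is significant and the 90% CI also lies inside ±0.10, either arm higher:

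| Uptake, % | ICC 0.05 | ICC 0.02 | ICC 0.01 |
|---|---|---|---|
| 15 vs 10 | 7-12% | 39-46% | 61-65% |
| 25 vs 20 | under 0.5% | 9-11% | 26-27% |
| 30 vs 25 | under 0.5% | 5% | 16-18% |

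With a 95% CI fewer trials pass the rule, so these shares would be lower.

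**5. Two worked results, 960 per arm, patient-directed vs enhanced.**
- Observed 25 vs 20%, ICC 0.01. Design effects 1 + 29 × 0.01 = 1.29 and 1 + 59 × 0.01 = 1.59. SE = √(0.1875 × 1.29/960 + 0.16 × 1.59/960) = 0.0227; t = 0.05/0.0227 = 2.20 on 39.7 df; p = 0.034. The 90% CI is +1.2 to +8.8 points. The 95% CI, 5.0 ± 2.02 × 2.27, is +0.4 to +9.6. The result is significant, yet either interval lies inside the margin.
- Observed 30 vs 24%, ICC 0.05. Design effects 2.45 and 3.95. SE = √(0.21 × 2.45/960 + 0.1824 × 3.95/960) = 0.0359; p = 0.10 on 35.3 df. The 90% CI is -0.1 to +12.1 points. The result is non-significant, yet equivalence is not shown.

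**6. Fisher's test with no true difference.** At 960 per arm and ICC 0.05 the average design effect is (2.45 + 3.95)/2 = 3.20. The nominal 1.96 is then worth 1.96/√3.20 = 1.10, a two-sided error of about 27%. Simulation of Fisher's test at 16-20% uptake gives about 25%.

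**The case against.** The best defence is that the analysis and sample-size paragraphs answer one form item and should be read together. The first says equivalence will be tested; the second supplies the scale, margin, test family and level. The general p-value criterion could apply to an equivalence test, and Fisher's test is described as a univariate look at association, not as the equivalence test. Part of this stands: the ingredients of a rule are in the document. But they appear only as what the calculations assume, and the analysis text names other procedures and never mentions the margin.

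A reader might infer that the plan will treat a non-significant p as equivalence, or a significant one as its failure. The documents say neither. The error rates above are therefore conditional on such a reading, and a significant difference inside the margin is a coherent result in itself.

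The false-equivalence risk also depends on uptake. At the low uptake that fits the stated power, the cluster-adjusted figure is 2-9%, and at 15 vs 5% it is below the CI rule's own error. Fisher's figure at 30 vs 20%, about 4%, is no worse than the rule's.

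Finally, the form asks only for a summary of methods, and the first page points to a published full protocol that was not available. That limits the claim to the supplied text.

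**Conclusion.** The point holds for the supplied text and should be fixed before an Aim 2 conclusion is reported. Equivalence is the goal and the basis of the sample size, but the margin and its test are not carried into the analysis, and the comparisons named there cannot establish it.

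The size depends on assumed uptake and ICC. A cluster-adjusted test read as equivalence when non-significant would be wrong in about 2-9% of trials at low uptake and 21-33% at 30 vs 20% to 50 vs 40% (ICC 0.05, true 10-point gap), against about 5% for a margin rule. The opposite conflict is the more robust one at low uptake, and it grows as the ICC falls. The authors think 0.05 is too high, though they give no other value. Fisher's disregard of clustering is a problem whichever way its p-value is read.

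Three stronger readings are not supported: that the sample size is wrong (its 80% is attainable at low uptake); that no equivalence rule exists anywhere (the published protocol was not seen); and that a 90% CI is already fixed (the 0.05 is not stated as per side or total). The 960 per arm is the planned figure, not an observed one.

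**What to change.** Make the primary Aim 2 analysis the cluster-adjusted difference in uptake, patient-directed minus enhanced. It could be standardised from a mixed logistic model, with clinic effects kept whatever the ICC test shows. Conclude equivalence only if the whole CI lies within -0.10 to +0.10. Use a 90% CI if the 0.05 in the sample size calculation was per side, or a 95% CI if it was total; state which, from the sizing record, and keep to it. Report Fisher's test and odds ratios as descriptive.

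The continuing review submitted on 1/4/2024 says analysis of primary outcomes was under way. Record that the rule was written after that point and whether arm-level uptake had been seen. The margin and scale are the plan's own; only the confidence level needs settling.

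For Aim 3 adherence, report the estimate and CI and do not claim pre-specified equivalence. Any margin shown there should be labelled post hoc.

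The cost is analysis text and a few lines of code, with no extra patients or data. If the published protocol already states such a rule, cite it and bring this text into line.
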